## 3.2 Analysis Populations

The following populations are defined:

**Table 2 Populations for Analysis** 

Population/Analysis set	Description
Enrolled	All participants who sign the ICF
All patients analysis set	All patients screened for the study, to be used for reporting of disposition and screening failures
Full analysis set (FAS)	All randomized patients who received at least 1 dose of investigational product (IP), irrespective of their protocol adherence and continued participation in the study.  Patients will be analyzed according to their randomized treatment irrespective of whether or not they have been given the incorrect IP or prematurely discontinued, according to the Intention to Treat principle. Patients who withdraw consent or assent to participate in the study will be

	included up to the date of their study termination.
Safety analysis set	The safety analysis set consists of all patients who have received at least one dose of investigational product.  Erroneously treated patients (eg, those randomized to one treatment but actually given the other treatment) are accounted for in the treatment group of the treatment they actually received.  A patient who has on one or several occasions received active investigational product is classified as active.  Safety summaries and anti-benralizumab antibody (immunogenicity) analyses will be based on this analysis set and for whom any post-dose data are available.
Pharmacokinetic analysis set	All patients who received benralizumab and from whom pharmacokinetic blood samples are assumed not to be affected by factors such as protocol violations (eg, received wrong dose) and who had at least 1 quantifiable serum pharmacokinetic observation post-first dose.  All pharmacokinetic summaries will be based on this analysis set.
Open-label benralizumab analysis set	All patients who receive at least 1 dose of benralizumab after the end of the Week 24 double-blind treatment period

## 3.3 General Considerations

The primary efficacy analyses will be based on the double-blind placebo-controlled first 24 weeks of the study (DB period). In this part of the study all efficacy analyses will use the full analysis set (FAS) as defined in Section 3.2, and patients will be analyzed according to their randomized treatment, following the Intent-to-Treat (ITT) principle.

A composite estimand strategy will be used for the primary analyses of endpoints at Week 24 whereby any patients who have required rescue corticosteroids, use of a restricted medication, or discontinued IP during the first 24 weeks will be considered as treatment failures at Week 24.

A review of all concomitant medications during the study will be performed prior to database lock to identify events to be considered as treatment failure in these analyses, whereby only medications considered likely to have a meaningful impact on EG/EGE outcomes would be considered intercurrent events. This could include addition of a new therapy or an increase in previously stable background medications to treat EG/EGE. For the histologic response rate endpoint, patients with these intercurrent events prior to Week 24 will be considered non-responders at Week 24; for the change from baseline in SAGED score at Week 24 endpoint, as well as other change from baseline continuous endpoints, any patients experiencing the described intercurrent events will have their worst observation (including baseline value) prior to or at the intercurrent event carried forward to Week 24.

All patients who prematurely discontinue from IP, use restricted medications, or have any changes to background therapies for EG/EGE as described above are asked to come in for all visits until they complete the overall study duration. Therefore, sensitivity analyses can be performed to assess the robustness of the efficacy results to these estimand approaches and missing data assumptions as described in individual endpoint analysis methods in Section 4.2.

The statistical analyses of the DB period are designed to compare both efficacy and safety of benralizumab to placebo, while the OLE period is designed to evaluate the long-term safety and tolerability and persistence of effect of benralizumab in this patient population. Details regarding primary and key secondary estimands with additional details including sensitivity analyses are provided in Section 4.2.

All analyses of part C of the study including week 52 endpoints will be descriptive as no placebo control is available at that timepoint and so no hypothesis testing will be performed. Week 52 analyses will primarily be presented on the FAS, but a repeat of key analyses may also be produced on the open-label benralizumab analysis set to ensure only patients who switched to receive benralizumab after 24 weeks are included in the denominator for that group and to ensure a meaningful interpretation of the placebo-to-benralizumab patients.

Demography and baseline characteristics will be summarized by treatment group for the FAS. In the event that there are major differences between the FAS and safety analysis set, these summaries may also be repeated for the safety analysis set.

Summary data will be presented in tabular format by treatment group. Categorical data will be summarized by the number and percentage of subjects in each category. Continuous variables

will be summarized by descriptive statistics including N, mean, SD, median, and range. Data listings will be sorted by treatment group and patient number.

All hypothesis testing will be reported using 2-sided tests. Any *p*-values presented for endpoints other than those included in the hierarchical testing strategy will be nominal (i.e., not multiplicity adjusted). All *p*-values will be rounded to 4 decimal places.

The data analyses will be conducted using the SAS® System version 9.4 or above (SAS Institute Inc., Cary, NC). All SAS® programs used to generate analytical results will be developed and validated according to AstraZeneca SAS® programming standards and validation procedures. Pharmacokinetic analyses will be performed using NONMEM or other appropriate software.

## 3.3.1 General Study Level Definitions

## 3.3.1.1 Study period definition

- **Double Blind (DB) period**: from the date of randomization up to the first dose of Open Label benralizumab 30 mg at Week 24, for both Part A and Part B subjects. If a participant does not transition into OLE then all the data will be included in the double-blind period.
- Open Label Extension (OLE) period: from the first dose of Open Label benralizumab 30 mg at Week 24 to the end of study, for the subjects who participated in Part C.

For all assessments scheduled at first dose date of OLE (V8, Week 24), the last recorded value on or prior to the first dose of OLE study treatment will be considered as in the double-blind period. If time is collected and relevant for the analysis, for example for PK or Biomarkers, only the assessments performed on the same day but at a time prior to the first dose of OLE study treatment will be included in the double-blind period.

When time of assessment is not recorded or missing, it is assumed that assessments recorded on the date of first dose of OLE study treatment were performed prior to dosing, except for Adverse Events which are defined in Section 4.6.2.1.

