1.3 Schedule of Activities

Table 1 presents the schedule of activities for Part A prior to approval of Amendment 4. Following approval of Amendment 4, all participants in Part A will directly proceed to Visit 20 of Part D (Table 3) at their next clinic visit.

	Run-in			D.	ubla b	linded	twoat-	ont novied		In case of disc	antinuation ⁸	CSP Section
	+		ı	1	ı			nent period				CSP Section
Visit (V)	V1	V2	V3	V4	V5	V6	V7	V8 /EOT ^b	Unscheduled ^c	IP Discontinuation	Follow-up	
Week	-8 to -4	0	4	8	12	16	20	24	-	4 weeks post- dose	8 weeks post- dose	
Visit Window (Days)			± 3	± 3	± 3	± 3	± 3	± 3		± 3	± 7	
General procedures				•					-			
Informed consent/assent	X	-	-	-	-	-	-	-	-	-	-	Appendix A 3
Demography/medical history	X	-	-	-	-	-	-	-	-	-	-	-
Inclusion/exclusion criteria	X	X	-	-	-	-	-	-	-	-	-	5.1, 5.2
Height, Weight	X	-	-	-	-	-	-	X	-	X	-	8.2.1
Efficacy assessments	1	•		•	•				-			1
Provide PRO device and instructions	X	-	-	-	-	-	-	-	-	-	-	8.1.3
Site visit PRO assessments (see Table 4)	X	X	-	-	-	-	-	X	-	X	-	8.1.3
Review PRO assessment compliance	-	X	X	X	X	X	X	X	-	X	-	8.1.3
Clinical Global Impression of Severity		X	-	-	-	-	-	X	-	X	X	8.1.4
Clinical Global Impression of Change	-		X	X	X	X	X	X	-	X	X	8.1.5
Diet questionnaire	X	X	X	X	X	X	X	X	Х	X	X	8.1.6

Qualitative interview reminde	-	X	-	-	-	-	-	-	-	-	-	8.1.7
Healthcare resource utilization	-	X	X	X	X	X	X	X	-	X	X	8.8
Endoscopy: biopsy, EG- REFS, and EREFS	Xe	-	-	-	-	-	-	X	-	X ^f	-	8.1.1, 8.1.2
Safety assessments												
Adverse events	X	X	X	X	X	X	X	X	X	X	X	8.3
Concomitant medication	X	X	X	X	X	X	X	X	X	X	X	6.5
Complete/(brief) physical exam	X	(X)	(X)	(X)	(X)	(X)	(X)	X	(X)	X	(X)	8.2.1
Vital signs	X	X	X	X	X	X	X	X	X	X	-	8.2.2
Electrocardiograms	-	X	-	-	-	-	-	-	-	-	-	8.2.3
Laboratory assessments		•										·
Hematology/clinical chem	X	-	-	X	-	X	-	X	-	X	X	8.2.4
Serology (hepatitis/HIV)	X	-	-	-	-	-	-	-	-	-	-	8.2.6
Urinalysis	X	-	-	-	-	X	-	X	-	X	-	8.2.4
Post-menopause confirmation ⁱ	X	-	-	-	-	-	-	-	-	-	-	8.2.5
Serum/(urine) pregnancy	X	(X)	-	(X)	(X)	8.2.5						
Pharmacokinetics	-	X	-	X	-	X	-	X	-	X	X ^h	8.5.1
Immunogenicity	-	X	-	X	-	X	-	X	-	X	X ^h	8.5.2
Biological sampling												·
Serum for total IgE	X	-	-	-	-	-	-	-	-	-	-	8.6.1.1
Serum for tryptase	X	-	-	-	-			X				
Blood, serum, plasma for biomarkers	X	-	-	X	-	X	-	X	-	-	-	8.6.1.1
Tissue for histopathology/biomarkers	X	-	-	-	-	-	-	X	-	X ^f	-	8.6.1.2

Blood for genetic analysis	-	X^k	ı	-	-	-	-	-	-	-	-	8.7
Investigational product adm	inistration											

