6.1.2 Duration and Frequency of Treatment with Investigational Products

Patients will receive investigational product (ie, benralizumab or matching placebo) Q4W. The investigational product will be administered on-site or, optionally, at home (see Sections 6.1.3.4 and 6.1.3.5). The acceptable visit windows are specified in the schedule in Section 1.3, and reasons and procedures for rescheduling investigational product administration are detailed in Section 6.1.3.3.

Prior to the approval of Amendment 4, patients who complete the 24-week double-blind treatment period are eligible to continue receiving benralizumab 30 mg Q4W in the open-label extension starting at Visit 8. The open-label extension treatment period was intended to allow patients at least 1-year treatment with open-label benralizumab 30 mg Q4W.

Following the approval of the protocol Amendment 4, patients in both Part A and Part C that are offered and choose to continue in Part D will be offered 24 weeks of open-label benralizumab Q4W treatment (ie, patients will not complete their current treatment period).

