9.4.3 Safety

Safety data presentations will be performed using the safety analysis set.

The first presentation of safety data will include only data from the double-blind, placebocontrolled first 24 weeks of the study (Part A double-blind period). Patients will be summarized according to the treatment they received (benralizumab or placebo).

Safety data from the open-label benralizumab parts of the study (Part C and Part D) will be reported separately from Part A.

Safety data will be presented using descriptive statistics, figures, and data listings. Full details will be provided in the SAP.

In general, the baseline value for safety analyses is the last non missing value prior to administration of the first dose of investigational product.

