#### 8 ADDENDUM

Protocol Version 5 (Amendment 4) was issued on March 28, 2023, after the decision to close recruitment to the study early. The amendment rationale was to fulfil a commitment to participants, from when they enrolled in the trial, of open-label access to benrazilumab following double-blind treatment.

Patients that completed Part A prior to approval of amendment 4 could choose to continue to Part C, an extended open-label benralizumab treatment period. Patients in Part A and Part C, after protocol amendment approval in their respective country, will be given the option at their next clinic visit of withdrawing from the study or moving on to Part D and receiving 6 months of open-label benralizumab Q4W dosing. Patients will not complete their current treatment period. Patients who have discontinued IP during Part A are not eligible to enter Part C or D.

Enrollment was terminated after enrollment of 34 participants, of which 12 were randomized. The figure below illustrates the current study design described above.

Figure 4 Study Design Flow Chart

Q4W: every fourth week; R: reference visit number of weeks (ie, visit prior to approval of Amendment 4); EoT: end of treatment; FU: follow-up.

Given the original sample size of the study will no longer be recruited and the study will be terminated, the analysis plan for the study was updated. The amended analysis plan will now consist of descriptive summaries of safety data and select patient listings of baseline characteristics, safety data, and key efficacy data for the double-blind placebo-controlled period (part A) and the open-label period (Parts C and D). Details on the descriptive summaries can be found below in Table 11.

Principles outlined in the main SAP document related to these descriptive summaries below will apply i.e. definition of periods for safety summaries. Other analyses described in the main SAP will no longer be implemented given the small final sample size limiting the ability to assess the original study objectives.

Table 11 List of summaries for the final analyses

Summaries	Period Period	Population	Format
Subject disposition	DB + OLE	All patients analysis set	Table
Duration of exposure	DB	Safety analysis set	Table
Duration of exposure	OLE	Open-label benralizumab analysis set	Table
Adverse events in any category	DB	Safety analysis set	Table
Adverse events in any category	OLE	Open-label benralizumab analysis set	Table

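### The SAP addendum keeps period definitions tied to Week 24 and Part C, which contradict its own open-label period for patients moving directly from Part A to Part D

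*SAP*

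**What the plan says.** Recruitment stopped with 12 patients randomised, and Amendment 4 added an open-label Part D. Protocol 1.3 states that after approval "all participants in Part A will directly proceed to Visit 20 of Part D (Table 3) at their next clinic visit". Protocol 6.1.2 adds that "patients will not complete their current treatment period".

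SAP Section 8 cuts the analysis down to the outputs in its Table 11. It names the periods covered as "the double-blind placebo-controlled period (part A) and the open-label period (Parts C and D". It also carries the older rules forward: "Principles outlined in the main SAP document related to these descriptive summaries below will apply i.e. definition of periods for safety summaries". Table 11 then labels each output DB, OLE or both, and does not define those labels again.

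The definitions it refers back to stand in these places:

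- **SAP 3.3.1.1, periods.** DB ends at the first open-label dose, placed at Week 24. OLE is defined as "first dose of Open Label benralizumab 30 mg at Week 24 to the end of study, for the subjects who participated in Part C". The default is: "If a participant does not transition into OLE then all the data will be included in the double-blind period".
- **SAP 3.3.1.1, same-day rule.** It opens with "For all assessments scheduled at first dose date of OLE (V8, Week 24".
- **SAP Table 2.** The open-label set needs a benralizumab dose after the Week 24 double-blind period has ended. Protocol Table 10 defines the same set with no mention of Week 24.
- **SAP 4.6.2.1.** Adverse events have their own rule. DB events stop the day before the first OLE dose, and OLE events start on the day of that dose. For patients who do not roll over, DB runs through V9.

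Protocol 9.4.3 states the intended reporting: "Safety data from the open-label benralizumab parts of the study (Part C and Part D) will be reported separately from Part A".

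**The concern.** A patient who goes directly from Part A to Part D never takes part in Part C and may take the first open-label dose before Week 24. That patient fails the Part C condition for OLE in 3.3.1.1 and, unless the move falls at Week 24, the timing condition too. The default then sends all of the patient's data to DB, while Section 8 and Protocol 9.4.3 call the same Part D data open-label.

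In Table 11 the key-information table for serious adverse events and both haematology/chemistry tables are produced for DB only. Under the literal rule, open-label results would enter tables meant for blinded treatment. The OLE exposure and OLE adverse-event tables use the open-label set, so a patient outside that set drops out of them. Two programmers could each cite the SAP and place the same event or sample in different periods.

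**Working it through.** The plan gives no figure on this point to reproduce. The check compares the rules and then applies the Part D schedule.

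**Which rule reaches which patient**

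- *Part A to C to D:* the first open-label dose was in Part C at Week 24. The 3.3.1.1 split is correct.
- *Part A, no open-label treatment:* the DB default in 3.3.1.1 is correct. The 4.6.2.1 cut-off is not usable, because Protocol Table 2 shows V9 as the Week 28 visit of Part C.
- *Part A directly to D:* under literal 3.3.1.1 there is no OLE period and everything is DB. Under Section 8 and Protocol 9.4.3, Part D is open-label. 4.6.2.1 gives the right split once Part D counts as OLE.

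**Schedule inputs**

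- Protocol Table 3: V20 is at R+4, where R is the week of the last visit before approval. Six doses follow at four-week intervals (V20 to V25). V26, the end-of-treatment visit, is at R+28. Haematology/chemistry is scheduled at V26, IP discontinuation and follow-up, not at V20 to V25.
- Protocol Table 1: post-baseline haematology/chemistry at Weeks 8, 16 and 24.
- SAP 4.6.2.1: on-treatment runs to the end-of-treatment visit inclusive.

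Let t = R+4 be the week of the first open-label dose. V20 replaces the Part A visit at Week t, so a Part A sample counts only if it was due before Week t. The values of R are assumed; the documents do not say when anyone moved.

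| Quantity | | | | | | |
|---|---|---|---|---|---|---|
| R | 0 | 4 | 8 | 12 | 16 | 20 |
| t = R+4 | 4 | 8 | 12 | 16 | 20 | 24 |
| Last Part D dose, t+20 | 24 | 28 | 32 | 36 | 40 | 44 |
| V26, t+24 | 28 | 32 | 36 | 40 | 44 | 48 |
| Part D doses before Week 24, (24−t)/4 | 5 | 4 | 3 | 2 | 1 | 0 |
| Blinded laboratory samples before Week t | 0 | 0 | 1 | 1 | 2 | 2 |
| On-treatment samples in the DB table, literal rule (add V26) | 1 | 1 | 2 | 2 | 3 | 3 |

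**Laboratory table.** For a Part D completer, one open-label sample enters the DB minimum/maximum table. For t = 4 or 8 it is the only scheduled post-baseline value. This count takes the on-treatment label in Table 11 and SAP 4.6.3.2 at face value. SAP 4.6.3.1 instead computes extremes over the whole post-baseline period. If the follow-up sample is then also taken, open-label samples are 2 of 2, 2, 3, 3, 4, 4. Protocol Table 3 allows that follow-up to be by telephone, so the sample may not exist.

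**Open-label set.** With Week 24 read as a calendar date, a patient who stops within the first 5, 4, 3, 2 or 1 Part D doses (t = 4 to 20) is outside the SAP set. At t = 4 the sixth dose falls at Week 24 itself. It counts only if a Week 24 dose is accepted, as in the original design, where open-label dosing began at that visit. At t = 24 the set is right, but 3.3.1.1 still excludes the patient from OLE because of the Part C condition.

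**After the fix.** With the switch at the first open-label dose in Part C or D, all six Part D doses and the 24 weeks from V20 to V26 are open-label for every R from 0 to 20.

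**The case against.** The strongest reply is that Section 8 already settles the matter. It is the later and more specific text, it equates DB with Part A and open-label with Parts C and D, and it introduces the table in which the labels are used. Protocol 9.4.3 agrees. What it carries forward are principles, which need not include every superseded reference to Week 24. The adverse-event rule cuts at the first OLE dose and mentions neither Week 24 nor Part C. Week 24 in SAP Table 2 can be read as a name for the double-blind period, which ends when the patient leaves Part A.

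Much of this stands. The intended split is clear enough to infer, and under it adverse events fall in the right period. It does not clear the wording, because the sentence in Section 8 that keeps the older rules names the period definitions as its example, and those definitions say something different.

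The reply on size also has force. No direct mover is documented. The largest laboratory shares (t = 4 or 8) need a patient randomised within about 8 weeks before local approval. Recruitment had closed before the amendment, and that version already reports the 12 randomised patients. This makes such cases less likely, although no dates exclude them.

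**Conclusion.** The point holds as a contradiction in wording. For any direct Part A to Part D patient, SAP 3.3.1.1 and Table 2 conflict with SAP Section 8, Protocol 9.4.3 and Protocol Table 10. Applied literally, 3.3.1.1 places Part D serious adverse events and the V26 sample in DB-only tables. The V9 cut-off is a separate fault and concerns only patients who do not roll over.

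A reader might infer more than the documents support:

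- *That direct movers have no valid split at all.* Section 8 and Protocol 9.4.3 supply one; the defect is that the retained definitions were not made to agree with it.
- *That the adverse-event rule fails for them.* It works once Part D is treated as OLE.
- *That DB exposure is overstated.* SAP 4.1.9.2 summarises exposure within each part. It does not name Part D, but an overcount cannot be shown from it.
- *That a treatment comparison is biased.* No hypothesis testing or comparison of arms is planned.

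The size is unknown: 0 to 12 direct movers, with timing not stated. The per-patient counts rest on assumed move weeks, on Part D completion and on the on-treatment reading. All outputs are descriptive, and adverse events and laboratory data are also listed by patient for both periods. Severity is minor.

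**What to change.** In SAP Section 8:

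1. Define DB as randomisation to immediately before the first open-label dose in Part C or Part D, at any week, and OLE as from that dose to the end of study.
2. Apply the same-day rule to the visit of that dose (V8 or V20).
3. Delete Week 24 from the SAP open-label set so that it matches Protocol Table 10.
4. Replace V9 in 4.6.2.1 with a visit that non-rollover patients have, such as the scheduled follow-up visit that the same section already uses to close the on-study period.

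The cost is SAP wording and the dataset derivations for period and open-label-set flags. No new data are needed.

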#### 3.3.1.2 Baseline definition

In general, the last non missing value on or prior to the date of randomization will serve as the baseline measurement for efficacy endpoints while the last non missing value prior to first dose of study treatment will serve as the baseline measurement for safety endpoints. If there is no value prior to the randomization (or the first dose of study treatment, depending on the endpoint), the baseline value will not be imputed and will be set to missing.

For the daily assessment variables including SAGED score and other daily symptoms scores which are calculated during a certain period (e.g., bi-weekly), the score calculated during the cycle prior to Baseline Visit 2 (Week 0) will be the baseline score.

For analyses re-setting baseline to the start of Part C, the baseline value is set to the last non missing value prior to the first dose of benralizumab in Part C (i.e., likely the Week 24 measurement).

